6.2.2. Post baseline Gram-Negative pathogen

If multiple records from the same parameter on the same date, the record with the highest quantitative for urine sample will be used.

6.2.3. Appropriate clinical specimens

Appropriate clinical specimens are defined as sputum, tracheal aspirate, bronchoalveolar lavage (BAL) fluid, protected specimen brush, pleural fluid, lung biopsy for HAP/VAP, blood for BSI/sepsis/cIAI, or urine for cUTI. Specimens that were collected from other sites may be considered as appropriate specimen. This will be determined by the medical monitor. If the infection site is "other", it will be determined whether the specimen is an appropriate clinical specimen or not by medical monitor. The time window of the 4 days prior to the first dose of cefiderocol will be determined based on time unit, ie within 5760 min from the first infusion.

Eligibility of subjects into the MITT Analysis Population will be based on local lab results of baseline pathogens if the microbiological culture results are not sent to a central lab for confirmation or if central lab results are missing. In addition, in such a case, the local lab result will be used for analysis.

6.2.4. Day 1

Day 1 will be defined as the day of the first dose of cefiderocol.

6.2.5. Study Day

For events that occur before the first dose of study drug, study day = date of the event – first dose date; for events that occur on or after the first dose of study drug, study day = date of the event – first dose date + 1. There will be no Day 0.

6.2.6. Nominal time

Nominal time will be defined as the scheduled measurement time relative to time 0. Time 0 will be the time of dosing for the treatment period of interest.

This document is confidential.

6.3. Handling of Microbiologic Data

If a pathogen is identified from local laboratory data but it is not sent to a central laboratory, the name reported by local laboratory will be used for analysis. In this case, the minimum inhibitory concentration (MIC) will be treated as unknown.

If a pathogen name is different between the local and central laboratory, the name assigned by the central laboratory will be used for the analysis. However, if the sample sent to International Health Management Associates Inc. (IHMA) was reported as “unknown” or the sample was not sent to IHMA, pathogen will be considered as no growth and used for analysis.

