5.5. Microbiological Intent-to-Treat Population (Multiple-dose Phase Only)

The Microbiological Intent-to-treat (MITT) Population will include all ITT subjects who have a baseline Gram-negative pathogen from any specimen from a baseline infection site.

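### SAP 6.3 gives opposite rules for a locally identified isolate not sent to the central laboratory, and one of them turns a positive local culture into 'no growth'

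*SAP*

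**What the plan says.** SAP 6.3 deals with an unsent isolate twice.

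- First paragraph: when a pathogen is identified locally but "it is not sent to a central laboratory, the name reported by local laboratory will be used for analysis". The MIC is then treated as unknown.
- Second paragraph: after giving the central name priority where the two laboratories disagree, it adds an exception that begins "However, if the sample sent to International Health Management Associates Inc. (IHMA) was reported as" 'unknown'. It then extends the exception to unsent samples: if "the sample was not sent to IHMA, pathogen will be considered as no growth and used for analysis".

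SAP 6.2.3 covers the same situation for the analysis population. Its trigger is a culture that was never forwarded for central confirmation, or a central finding that is absent. Its rule is then: "Eligibility of subjects into the MITT Analysis Population will be based on local lab results of baseline pathogens". It adds that "in such a case, the local lab result will be used for analysis".

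SAP 5.5 defines MITT as "all ITT subjects who have a baseline Gram-negative pathogen from any specimen from a baseline infection site". SAP section 8 defines eradication as absence of the baseline pathogen or, in cUTI, a fall to below 10^3 CFU/mL. Protocol 7.5.3.2 has local laboratories identify the pathogens and says isolates from the multiple-dose phase should be sent to the central laboratory.

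**The concern.** An isolate that was grown and named locally but not shipped falls under two instructions that cannot both be programmed. One keeps the organism and the other erases it. The erasing rule has no microbiological basis: failure to ship says nothing about whether the culture grew.

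Two things are at stake. At baseline, the rule decides who is in MITT, the only population for the microbiological outcome tables and one of the two for clinical outcome. After baseline, an organism that is still present could satisfy the definition of eradication. Both bear on the microbiological half of the single secondary objective (cefiderocol given alone) and on the exploratory microbiological objective.

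The rule also fits poorly with SAP 6.4, which names only 6.4.1 and 6.4.2 as places where missing data are imputed. SAP 6.4.2 counts missing outcomes as non-response, whereas a post-baseline 'no growth' points towards response.

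**Working it through.** **Step 1. The rules side by side.**

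| Situation | 6.3, paragraph 1 | 6.2.3 | 6.3, paragraph 2 |
|---|---|---|---|
| Isolate not sent | Local name, MIC unknown | Local result for MITT entry and analysis | 'No growth' |
| Sent, central result missing | Silent | Local result for MITT entry and analysis | Silent |
| Sent, IHMA reports 'unknown' | Silent | Local result only if 'unknown' counts as missing (not defined) | 'No growth' |

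The contradiction is direct in the first row. In the third row it depends on an undefined term, although recoding a positive local culture as negative is unjustified there too. No text ranks the rules or limits paragraph 2 to baseline or to post-baseline cultures.

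**Step 2. Can a narrower reading remove the conflict?** Two were tried.

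- Paragraph 2 might apply only where the local and central names differ. A sample that was never sent has no central name to differ, so this does not explain the not-sent clause.
- IHMA might be a different laboratory from the central one. SAP 6.2.1 ties susceptibility testing to pathogens identified by IHMA, and 6.3 uses IHMA in the sentence that follows the central-laboratory rule. The documents do not support a separation.

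**Step 3. Effect at baseline, if paragraph 2 is applied over 6.2.3.** A subject whose only baseline Gram-negative isolate is affected no longer meets the MITT definition. Illustration, with assumed counts: 30 subjects, 21 eradicated, 3 subjects lost.

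- Before the loss: 21/30 = 70.0%.
- All three lost were failures: 21/27 = 77.8%.
- All three lost were successes: 18/27 = 66.7%.

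The direction is therefore not fixed.

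**Step 4. Effect after baseline.** If k persistences among n subjects are recoded as eradication, the rate rises by 100 × k/n percentage points. The planned minimum gives n = 10 per multiple-dose cohort and 3 × 10 = 30 overall (SAP 3.4).

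| k | n = 10 | n = 30 |
|---|---|---|
| 1 | 10.0 | 3.3 |
| 2 | 20.0 | 6.7 |
| 3 | 30.0 | 10.0 |

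The table assumes that every subject in a minimum-size cohort is in MITT. Entry allows merely suspected infection, so MITT may be smaller, and the cefiderocol-alone subset smaller again. The shift per case, 100/n, then grows. The documents do not say how many isolates were unsent or reported as 'unknown', so k is an assumption throughout.

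**Step 5. Where the post-baseline effect can occur.** Under SAP section 8, the per-subject outcome is the investigator's eCRF entry, and a non-cUTI subject with clinical cure at the visit already counts as eradicated. That leaves mainly per-pathogen outcomes derived by program (the SAP does not state their source), cUTI, and non-cUTI subjects without clinical cure.

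**The case against.** The strongest reply is that the consequences are narrower than the wording of paragraph 2 suggests. Much of it stands.

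- A reader might infer that documented persistence will be reported as success. The documents do not establish this. The investigator enters persistence when any baseline pathogen persists, and nothing says that 6.3 overwrites the entry. The per-pathogen tables remain exposed, and protocol 7.6.2.1 bases the per-subject outcome on the individual pathogen outcomes, so the risk is conditional but not closed.
- A reader might infer that the bias always favours the drug. Only the post-baseline route has that direction. Loss from MITT can go either way, and nothing indicates that unsent isolates come mainly from failures.
- Exclusion from MITT is not certain. SAP 6.2.3 is the rule written specifically for MITT eligibility, and a programmer could reasonably let it prevail. The SAP does not say so.
- Efficacy is descriptive here. No inferential testing is planned, and protocol 7.7 says the efficacy assessments are deliberately not rigorous.

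These points limit size and severity. None of them reconciles the two paragraphs of 6.3 for an unsent isolate.

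**Conclusion.** The inconsistency is real and should be fixed, but it does not threaten the study's main conclusions. For unsent isolates, SAP 6.3 contradicts itself and its second paragraph contradicts 6.2.3. For isolates that IHMA reports as 'unknown', conflict with 6.2.3 depends on whether that means a missing central result. In both branches the 'no growth' assignment is wrong as a description of a positive local culture.

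The size cannot be estimated from the documents. The 10-point and 3.3-point shifts per case assume that all subjects in minimum-size cohorts are in MITT, that paragraph 2 is the rule programmed, and that the affected outcome is not taken from the investigator's entry. The effect is confined to the descriptive secondary and exploratory efficacy results and to MITT membership. The primary safety and PK objectives are unaffected.

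**What to change.** Delete the 'no growth' sentence from SAP 6.3 and replace it with one rule, for baseline and post-baseline cultures alike:

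*Where an isolate was not sent to the central laboratory, or the central result is missing or 'unknown', the local identification and count are used and the MIC is set to unknown. 'No growth' is assigned only where the culture itself was reported as no growth. This rule does not override the microbiological outcome entered by the investigator in the eCRF.*

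State also whether per-pathogen outcomes come from the eCRF or are derived from culture records.

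The cost is a short SAP edit and one derivation rule before database lock. No new data are needed: protocol 7.5.3.2 already has local culture results for the multiple-dose phase recorded in the eCRF.

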6.4. Missing Data

In general, missing data will not be imputed. All analyses will be based on observed cases. Sections 6.4.1 and 6.4.2 note the situations where missing data will be imputed.

6.4.1. Handling of Missing Dates/Months/Years for Prior/Concomitant Therapies

If the medication cannot be classified into concomitant medications or prior medications due to incomplete date, the rules below will be applied for the classification.

For start date,

- If the year and month are observed but the day is missing, the first day of the month will be used unless the month and year are the same as the month and year of first dose date, then the day of first dose date will be imputed.
- If the year is observed but the month and day are missing, the first day of the year, 01 Jan, will be used unless year is the same as first dose date, then the first dose date will be used
- If the start date is completely missing, the medication will be considered concomitant unless the stop date is before study drug administration.
- If the start and stop dates are both completely missing, a therapy will be considered concomitant.
- If the year is observed but the time is missing, the first time of the day, 00:00 AM will be used.
- If the end date is complete and the imputed start date is after the stop date, then the start date will be imputed using the stop date.

For end date,

- If the year and month are observed but the day is missing, the last day of the month will be used unless the month and year are the same as the month and year of last dose date, then the last dose date will be imputed.
- If the year is observed but the month and day are missing, the last day of the year, 31 Dec, will be used unless the year is the same as the last dose date, then the last dose date will be used.
- If the end date is completely missing and the medication is still ongoing, then the missing end date will not be imputed. If the medication is not ongoing and the start date is prior to the first dose date, the end date will be imputed using the first dose date.
- If both start and end dates are completely missing, medication will be considered concomitant.
- If the year is observed but the time is missing, the end time of the day, 23:59 PM will be used.
- If the imputed end date is before the start date (imputed or non-imputed start date), then the stop date will be imputed using the start date.

The original partial or missing date will be shown in listings for all prior and concomitant medications.

This document is confidential.

6.4.2. Missing Microbiological or Clinical Outcome

For clinical and microbiological outcomes, subjects who are lost to follow-up or have missing or “indeterminate” outcomes will be included in the denominator as indeterminate for cure/eradication rate, ie, considered as nonresponders.

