- j Multiple doses of cefiderocol administered as an IV infusion over 3 hours, q8h, beginning on Day 1 and continuing for an expected 5 to 14 days. Note: Shorter infusion times may be allowed in the multiple-dose phase if agreed on by the sponsor and in the best interest of the subject via the Request for Shortened Infusion Duration Form. In special circumstances, treatment beyond 14 days may be allowed following review and approval of individual cases by the Shionogi medical monitor via the Treatment Extension Form.
- k Cohort 2: Blood samples will be collected once at each time point: at 1, 3 (within 15 minutes prior to the end of infusion using a separate line or immediately after the end of infusion using the same line and with proper flushing), 3.5, 5, and 8 hours after the start of infusion for the single dose and Cohort 2 for the multiple dose phase during one of the dosing intervals from the 6th to the 12th dose of cefiderocol. Pharmacokinetic sampling schedule is shown in [Table 7-2](#).
- l Cohorts 3 and 4: Blood samples will be collected once at each time point at 3 (within 15 minutes prior to the end of infusion using a separate line or immediately after the end of infusion using the same line and with proper flushing), 5, and 8 hours after the start of infusion for the single dose and during one of the dosing intervals from the 6th to the 12th dose of cefiderocol during the multiple dose phase. Pharmacokinetic sampling schedule is shown in [Table 7-2](#).
- m Clinical outcome assessments will be performed at EOT, Posttreatment, and EOS if available; additional clinical outcome assessments may be performed as part of routine patient care.

-
- n Microbiological specimens may be collected as part of routine patient care and time points are not otherwise prespecified per protocol (EOT, Posttreatment Visit, and EOS, if applicable). In subjects where it is not possible to obtain a posttreatment culture and/or EOS culture, determination of presumed microbiological eradication maybe made based resolution of all presenting clinical sign and symptoms of the infection (clinical cure).

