3.2. Secondary Objective

- Multiple-dose phase only: Whenever cefiderocol is administered alone, to assess the clinical response at the Posttreatment visit (7 [±4] days following End of Treatment [EOT]) and at the End-of-study (EOS) visit, AND to assess the microbiological response at the Posttreatment visit (7 [±4] days) following EOT and EOS (if available)

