7.5.2. Concomitant Therapy

Concomitant therapy (Concomitant antibiotic therapy, Concomitant Standard of Care Treatment for Disease, Concomitant Non-Antibiotic therapy) is defined as any therapy administered after study drug is administered in the study.

This document is confidential.

8. Efficacy

Efficacy endpoints will be evaluated for subjects in the multiple-dose phase of the study for the ITT and MITT analysis Populations.

The efficacy endpoints are as follows:

- Clinical outcome, defined as the categories below:

HAP/VAP/cIAI:

- Clinical Cure: Resolution or substantial improvement of baseline signs and symptoms of pneumonia/cIAI.
- Clinical Failure: No apparent response to therapy; persistence or worsening of baseline signs and/or symptoms of pneumonia/cIAI; reappearance of signs and/or symptoms of pneumonia/cIAI; development of new signs and/or symptoms of pneumonia/cIAI requiring antibiotic therapy other than, or in addition to, study drug therapy; progression of chest radiographic abnormalities; or death due to pneumonia/cIAI.
- Indeterminate: Lost to follow-up such that a determination of clinical cure/failure cannot be made.

cUTI:

- Clinical Cure: Resolution or substantial improvement of baseline signs and symptoms of cUTI, or return to pre-infection baseline if known, such that no antibiotic therapy is required for the treatment of the current infection.
- Clinical Failure: No apparent response to therapy; persistence or worsening of baseline signs and/or symptoms of cUTI; or reappearance of signs and/or symptoms of cUTI; development of new signs and/or symptoms of cUTI requiring antibiotic therapy other than, or in addition to, study drug therapy; or death due to cUTI.
- Indeterminate: Lost to follow-up such that a determination of clinical cure/failure cannot be made.

BSI/Sepsis:

- Clinical Cure: Resolution or substantial improvement of baseline signs and symptoms. Subjects with bacteremia must have eradication of bacteremia caused by the Gram-negative pathogen.
- Clinical Failure: No apparent response to therapy; persistence or worsening of baseline signs and/or symptoms, reappearance of signs and/or symptoms; development of new signs and/or symptoms requiring antibiotic therapy other than, or in addition to, study drug therapy; or death due to BSI/sepsis.
- Indeterminate: Lost to follow-up such that a determination of clinical cure/failure cannot be made.

This document is confidential.

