8.1. Efficacy Endpoints and Analyses

8.1.1. Clinical Outcomes

For subjects treated with cefiderocol alone, the number and proportion of subjects in each category will be calculated for each time point (EOT and Posttreatment visit and at EOS). Subjects will be presented by cohort and overall, for the ITT and MITT Populations. Note that the study is not designed to collect outcome data at EOS on all subjects, and summaries for Clinical Outcomes will be underestimated due to indeterminate caused by missing data.

For subjects treated with cefiderocol alone, the number and proportion of subjects in each category and each baseline Gram-negative pathogen will be calculated for each time point (EOT, and Posttreatment visit and at EOS). Subjects will be presented by cohort and overall, for the MITT Population.

In addition, the proportion of clinical cure rate at Post treatment visit by each baseline pathogen and MIC will be calculated.

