8.2. Exploratory Efficacy Endpoints and Analyses

8.2.1. Clinical Outcomes

For subjects treated with cefiderocol in combination with SOC, the number and proportion of subjects in each category will be calculated for each time point (EOT, Posttreatment and EOS). Subjects will be presented by cohort and overall, for the ITT and MITT Populations. The same analysis will be performed for subjects with cefiderocol + SOC and all subjects treated with cefiderocol.

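### SAP 6.4.2 counts a missing later clinical outcome as indeterminate even after a recorded clinical failure, which understates the failure proportion at Posttreatment and EOS

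*SAP*

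**What the plan says.** SAP 6.4 opens with the general position that "In general, missing data will not be imputed", and names 6.4.1 and 6.4.2 as the exceptions. SAP 6.4.2 is the exception for outcomes: subjects who are lost, missing or indeterminate "will be included in the denominator as indeterminate for cure/eradication rate, ie, considered as nonresponders". Nothing there, or elsewhere in the SAP, treats a child with an earlier clinical failure differently.

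SAP section 8 defines the clinical category Indeterminate, for every infection type, as "Lost to follow-up such that a determination of clinical cure/failure cannot be made".

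All categories are tabulated at EOT, Posttreatment and EOS. For children on cefiderocol alone, SAP 8.1.1 adds that "the number and proportion of subjects in each category and each baseline Gram-negative pathogen will be calculated for each time point". For the exploratory tables, SAP 8.2.1 states: "The same analysis will be performed for subjects with cefiderocol + SOC and all subjects treated with cefiderocol". The Posttreatment visit carries the secondary objective: "Multiple-dose phase only: Whenever cefiderocol is administered alone, to assess the clinical response at the Posttreatment visit". Protocol 3.1 describes that visit as analogous to test of cure.

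On availability, the notes to Protocol Appendix 1 state: "Clinical outcome assessments will be performed at EOT, Posttreatment, and EOS if available". SAP 8.1.1 warns that EOS outcomes are not collected on everyone and that "summaries for Clinical Outcomes will be underestimated due to indeterminate caused by missing data".

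On the side point, Protocol 6.2.1 says that hemodialysis started on study should lead to subject withdrawal, and refers only to Section 4.3.

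**The concern.** A child whose treatment has been rated a failure at EOT, and who is not assessed again, is not someone about whom nothing is known. Under SAP 6.4.2 that child nevertheless joins the children of unknown outcome at Posttreatment and EOS. A reader of the Posttreatment table cannot tell the two apart.

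The situation is foreseeable. Protocol 4.5 lists progression of the infection as a reason to stop treatment. For a child so stopped, with consent intact, it secures EOT procedures and AE reporting to EOS. It does not name the Posttreatment clinical outcome. Children who fail may therefore be among those whose later outcome is least secure.

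At stake is the failure proportion at the visit named in the secondary objective (cefiderocol alone) and in the exploratory tables (combination and all subjects).

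**Working it through.** **Planning figure.** The cohort minimums are 4 × 6 = 24 (single dose) and 3 × 10 = 30 (multiple dose), and 24 + 30 = 54, which reproduces the stated minimum. Efficacy uses only the multiple-dose children, so the denominators are at least 10 per cohort and 30 overall. There is no power calculation to reproduce.

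**Shift per affected child.** Take a child with failure at EOT and no later outcome. At Posttreatment the SAP rule adds 1 to indeterminate and 0 to failure. Carrying the failure forward adds 1 to failure and 0 to indeterminate. The difference in the failure proportion is 1/n, and the difference in the cure proportion is 0.

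| n | Source of n | Shift in failure (points) |
|---|---|---|
| 30 | all multiple-dose children, minimum | 3.3 |
| 10 | one cohort, minimum | 10.0 |
| 5 | assumed, e.g. cefiderocol-alone set | 20.0 |
| 3 | assumed, e.g. one pathogen row | 33.3 |

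**Illustration at Posttreatment (all counts assumed).**

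- n = 10, with 6 cures, 2 children who failed at EOT and are now missing, and 2 others missing. Cure is 6/10 = 60% either way. Failure is 0/10 = 0% under the SAP and 2/10 = 20% with carry-forward. Indeterminate is 4/10 = 40% and 2/10 = 20%.
- n = 30, with 20 cures, 3 such children, 2 observed failures and 5 others missing. Cure is 20/30 = 66.7% either way. Failure is 2/30 = 6.7% and 5/30 = 16.7%. Indeterminate is 8/30 = 26.7% and 5/30 = 16.7%.

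**How often.** The documents give neither a failure rate nor a missingness rate. Assume an EOT failure rate f of 5% to 20%, and that a share m of 10% to 50% of failures have no later outcome. The chance per child is p = f × m, the expected number in 30 is 30p, and the chance of at least one in n is 1 − (1 − p)^n.

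| f, m | p | Expected in 30 | At least one in 10 | At least one in 30 |
|---|---|---|---|---|
| 0.05, 0.10 | 0.005 | 0.15 | 1 − 0.995^10 = 5% | 1 − 0.995^30 = 14% |
| 0.10, 0.30 | 0.03 | 0.9 | 1 − 0.97^10 = 26% | 1 − 0.97^30 = 60% |
| 0.20, 0.50 | 0.10 | 3.0 | 1 − 0.90^10 = 65% | 1 − 0.90^30 = 96% |

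The range is too wide to predict whether the case will occur. It shows only that it cannot be dismissed.

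**Microbiological outcome.** SAP section 8 lists absence of a culture among the grounds for Indeterminate, so 6.4.2 agrees with that definition and the point does not extend to it.

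**Hemodialysis.** Protocol 4.5 ends assessments only when consent or assent is withdrawn. Otherwise it gives EOT procedures and AE reporting to EOS to a child taken off study treatment. Protocol 7.5.4.2 asks for AE collection after either kind of stop. Protocol 4.5 does not name the Posttreatment visit, although the multiple-dose notes to Appendix 1 make laboratory tests mandatory there. No rate is given, so no figure is offered.

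**The case against.** The strongest reply is that outcomes are rated visit by visit. With no Posttreatment assessment, the outcome at that visit really is unknown. SOC antibiotics can be changed at any time (Protocol 5.1.2), so a child who failed at EOT might later recover. Carry-forward is itself an imputation, in a plan that mostly avoids imputing. The SAP already takes the cautious route by counting missing as nonresponse, and only the split between two visible nonresponder rows moves. No hypothesis is tested, Protocol 7.7 describes the efficacy assessments as deliberately not rigorous, and the SAP discloses the effect of missing EOS outcomes.

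Much of this stands, and it rules out three stronger readings that a reader might infer:

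- **That the SAP overwrites the failure rating.** It does not. The EOT rating remains in the EOT table and in the listings; only the later visit is set to indeterminate.
- **That 6.4.2 contradicts the SAP's own definition.** It is wider than the section 8 definition, but a contradiction would need a rule that failure at one visit settles the next. The SAP has none; it is silent on the matter.
- **That the cure rate is affected.** It is not.

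The reply does not remove the remaining gap. The failure proportion is a reported result in its own right. The disclosure in 8.1.1 concerns EOS and not Posttreatment. When nothing later has been observed, the recorded failure is the best information available, and a carry-forward limited to that case does not deny later recovery where it is seen.

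On hemodialysis, a reader might infer that follow-up ends. Protocol 4.5 and 7.5.4.2 do not support that.

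**Conclusion.** The point holds in a limited form. Read literally, SAP 6.4.2 moves a child with a known clinical failure and no later outcome into the indeterminate row at Posttreatment and EOS. Each such child lowers the reported failure proportion by 1/n: 10.0 points in a cohort of 10, 3.3 points in 30, and more in smaller sets whose size the documents do not give.

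The conclusion rests on one judgement: that an earlier failure should stand when nothing later is observed. The effect is modest because the analysis is descriptive, efficacy is not primary, the cure rate is untouched, and the number of affected children is unknown. It concerns the secondary objective only for children on cefiderocol alone. The correction is still worth making, because it is cheap and affects the visit that the secondary objective names.

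The hemodialysis wording is a minor ambiguity. The event should be rare, given the renal and critical-illness exclusions in Protocol 4.3.

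**What to change.** Add to SAP 6.4.2: *If the clinical outcome at Posttreatment or EOS is missing or indeterminate, a clinical failure at EOT is carried forward to Posttreatment and EOS, and a clinical failure at Posttreatment is carried forward to EOS. An observed later cure or failure is not overridden. The rule for microbiological outcome is unchanged.*

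Protocol 9.4 leaves missing-data handling to the SAP, so this needs no protocol change. Because the study is open label, the rule should be settled before database lock and without reference to the outcomes. The downside is that failure proportions may look slightly less favourable.

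Minor, in Protocol 6.2.1: replace *subject withdrawal* with *permanent discontinuation of cefiderocol; unless consent or assent is withdrawn, EOT procedures, the Posttreatment visit (including mandatory laboratory tests and clinical outcome, multiple-dose phase) and EOS follow-up are completed per Appendix 1*. The visits should be named directly, because a reference to Section 4.5 alone would not secure Posttreatment. This adds no visit to the schedule. As a protocol edit it needs ethics approval (Protocol 10.10), so it can wait for the next amendment.
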